11.3 Vital Signs

Descriptive statistics for height, vital signs (ie, temperature, body weight, respiratory rate, and supine pulse rate, supine systolic and diastolic BP) and changes from baseline values at each assessment time point will be presented by study intervention group.

Vital sign values will be considered PCS if they meet both the observed-value criteria and the change-from-baseline criteria listed in [Table 11-2](#). The number and percentage of participants with PCS postbaseline values will be tabulated by study intervention group for the double-blind Intervention Period and Postintervention Period separately. The percentages will be calculated relative to the number of participants with available non-PCS baseline values and at least 1 postbaseline assessment in the specific period. The numerator will be the total number of participants with available non-PCS baseline values and at least 1 PCS postbaseline value during the specific period. A supportive tabular display of participants with PCS postbaseline values will be provided, including the PID number, baseline and all postbaseline (including non-PCS) values.

In addition, a tabular display showing all AEs that occurred in participants who had PCS postbaseline vital sign values will be provided.

Table 11-2. Criteria for Potentially Clinically Significant Vital Signs

Parameter	Flag	Criteria ^a	
		Observed Value	Change From Baseline
Systolic Blood Pressure, mmHg - Postural Vital Signs (Supine and Standing)		Decrease in systolic blood pressure of 20 mmHg or more from supine to standing [*Change from supine SBP \leq -20]	Decrease in systolic blood pressure from supine to standing at observed time point is at least 10 mmHg greater than the decrease in systolic blood pressure from supine to standing at baseline [Postbaseline change from supine SBP – baseline change from supine SBP \leq -10]
Diastolic Blood Pressure, mmHg Postural Vital Signs (Supine and Standing)		Decrease in diastolic blood pressure of 10 mmHg or more from supine to standing [Change from supine DBP \leq -10]	Decrease in diastolic blood pressure from supine to standing at observed time point is at least 10 mmHg greater than the decrease in diastolic blood pressure from supine to standing at baseline [Postbaseline change from supine DBP – baseline change from supine DBP \leq -10]
Pulse Rate, bpm - Postural Vital Signs (Supine and Standing)		Increase in heart rate of 20 beats per minute or more from supine to standing [Change from supine pulse rate \geq 20]	Increase in heart rate from supine to standing at observed time point is at least 10 beats per minute greater than the increase in heart rate from supine to standing at baseline [Postbaseline change from supine pulse rate – baseline change from supine pulse rate \geq 10]
Systolic Blood Pressure, mm Hg (Supine)	High	Age 6-11 (inclusive): \geq 140 Age 12-17 (inclusive): \geq 155	Increase of \geq 20
	Low	Age 6-11 (inclusive): \leq 80 Age 12-17 (inclusive): \leq 90	Decrease of \geq 20
Diastolic Blood Pressure, mm Hg (Supine)	High	Age 6-11 (inclusive): \geq 95 Age 12-17(inclusive): \geq 105	Increase of \geq 15
	Low	Age 6-11 (inclusive): \leq 40 Age 12-17 (inclusive): \leq 45	Decrease of \geq 15
Pulse Rate, bpm (Supine)	High	Age 6-11 (inclusive): \geq 140 Age 12-17 (inclusive): \geq 120	Increase of \geq 15
	Low	Age 6-11 (inclusive): \leq 50 Age 12-17 (inclusive): \leq 40	Decrease of \geq 15
Weight, kg	High	—	Increase of \geq 5%
	Low	—	Decrease of \geq 5%

a. A postbaseline value is considered potentially clinically significant if it meets both the observed value and the change from baseline criteria.

bpm = beats per minute; DBP = diastolic blood pressure; SBP = systolic blood pressure.

* Change from supine value = standing value – supine value

11.4 Electrocardiogram

Descriptive statistics for ECG parameters (ventricular heart rate, RR interval, PR interval, QRS interval, QT interval, and QTc) and changes from baseline values at each assessment time point will be presented by study intervention group. The QTc will be calculated using both the Bazett and Fridericia corrections.

Electrocardiographic parameter values are considered PCS if they meet or exceed the higher-limit PCS criteria listed in [Table 11-3](#). The number and percentage of participants with PCS postbaseline ECG values will be tabulated by study intervention group for the double-blind intervention period. The percentages will be calculated relative to the number of participants with available non-PCS baseline values and at least 1 postbaseline assessment for the double-blind Intervention Period. The numerator is the total number of participants with available non-PCS baseline values and at least 1 PCS postbaseline value for the double-blind Intervention Period. A supportive tabular display of participants with PCS postbaseline values will be provided, including the PID number, baseline, all postbaseline (including non-PCS) values, and change from baseline. In this listing, any participant with PCS value (if any) during Postintervention Period will also be included.

In addition, a tabular display showing all AEs that occurred in participants who had postbaseline PCS ECG values will be provided.

A shift table from baseline to the end of double-blind Intervention Period in the Investigator’s overall interpretation of the ECG will be presented by study intervention group for the following categories: normal; abnormal, not clinically significant; abnormal, clinically significant. A tabular display showing participants with postbaseline clinically significant ECG abnormalities according to the Investigator’s overall interpretation will be provided.

Table 11-3. Criteria for Potentially Clinically Significant Electrocardiograms

Parameter	Unit	Higher Limit
QRS interval	msec	QRS \geq 115 msec (6-7 (inclusive) years) QRS \geq 125 msec (8-15 (inclusive) years) QRS \geq 150 msec (16-17 (inclusive) years)
PR interval	msec	PR > 225 msec (6-7 (inclusive) years) PR > 250 msec (8-17 (inclusive) years)
QTc(F)	msec	>480

QTc(F) QT Corrected by Fridericia’s formula

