11.2 Clinical Laboratory Parameters

Descriptive statistics for clinical laboratory values (in International System of Units [SI] units) and changes from the baseline values at each assessment time point will be presented by study intervention group for the following laboratory parameters:

Hematology: Absolute and differential white blood cell count, erythrocyte count, hemoglobin, hematocrit, platelet count, red blood cell count, and red blood cell indices (mean corpuscular volume, mean corpuscular hemoglobin, and mean corpuscular hemoglobin concentration)

Chemistry: Sodium, potassium, calcium, chloride, bicarbonate, magnesium, phosphate, glucose, blood urea nitrogen, creatinine, total protein, alkaline phosphatase (ALP), albumin, total bilirubin (TBL), alanine aminotransferase (ALT), aspartate aminotransferase (AST), total cholesterol

Urinalysis: Specific gravity and pH

Clinical laboratory test values will be considered potentially clinically significant (PCS) if they meet either the lower-limit or higher-limit PCS criteria listed in [Table 11-1](#). The number and percentage of participants who have PCS postbaseline clinical laboratory values will be tabulated by study intervention for the double-blind Intervention Period. The percentages will be calculated relative to the number of participants with available non-PCS baseline values and at least 1 postbaseline assessment for the double-blind Intervention Period. The numerator will be the total number of participants with available non-PCS baseline values and at least 1 PCS postbaseline value for the double-blind Intervention Period. A supportive tabular display of participants with PCS postbaseline values will be provided, including the PID number, baseline

and all postbaseline (including non-PCS) values. In this listing, any participant with PCS value (if any) during the Post-intervention period will also be included.

In addition, a tabular display showing all AEs that occurred in participants who had PCS postbaseline clinical laboratory values will be provided.

Shift tables from baseline to the end of double-blind Intervention Period for clinical laboratory parameters listed above will be presented by study intervention group for the following categories: low, normal, and high, which are provided by lab vendor.

Table 11-1. Criteria for Potentially Clinically Significant Laboratory Results

Parameter	SI Unit	Lower Limit	Higher Limit
CHEMISTRY			

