Albumin	g/L	< 0.9 × LLN	> 1.1 × ULN
Alanine aminotransferase (ALT)	U/L	—	≥ 3 × ULN
Alkaline phosphatase	U/L	—	≥ 1.2 x ULN: 6-12 (inclusive), male & female; 13-15 (inclusive), male ≥ 3 × ULN: 13-15 (inclusive), female; 16- 17 (inclusive), male & female
Aspartate aminotransferase (AST)	U/L	—	≥ 3 × ULN
Bicarbonate	mmol/L	< 0.9 × LLN	> 1.1 × ULN
Bilirubin, total	µmol/L	—	> 1.5 × ULN
Calcium	mmol/L	< 0.9 × LLN	> 1.1 × ULN
Chloride	mmol/L	< 0.9 × LLN	> 1.1 × ULN
Cholesterol, Total	mmol/L	—	> 1.6 × ULN
Creatinine	µmol/L	—	> 1.3 × ULN
Glucose, random, serum	mmol/L	< 0.8 × LLN	> 1.4 × ULN
Potassium	mmol/L	< 0.9 × LLN	> 1.1 × ULN
Protein, total	g/L	< 0.9 × LLN	> 1.1 × ULN
Sodium	mmol/L	< 0.9 × LLN	> 1.1 × ULN
Urea Nitrogen (BUN)	mmol/L	—	> 1.2 × ULN
HEMATOLOGY			
Basophils, absolute cell count	10 ⁹ /L	—	> 3 × ULN
Eosinophils absolute cell count	10 ⁹ /L	—	> 3 × ULN
Lymphocytes absolute cell count	10 ⁹ /L	< 0.7 × LLN	> 1.3 × ULN
Monocytes, absolute cell count	10 ⁹ /L	< 0.5 × LLN	> 2.0 × ULN
Neutrophils, absolute cell count	10 ⁹ /L	< 0.8 × LLN	> 1.5 × ULN
Hematocrit	Ratio	< 0.9 × LLN	> 1.1 × ULN
Hemoglobin	g/L	< 0.9 × LLN	> 1.1 × ULN
Platelet count	10 ⁹ /L	< 0.5 × LLN	> 1.5 × ULN
Red blood cell count	10 ¹² /L	< 0.9 × LLN	> 1.1 × ULN
White blood cell count	10 ⁹ /L	< 0.7 × LLN	> 1.5 × ULN
URINALYSIS			
pH	—	< 0.9 × LLN	> 1.1 × ULN
Specific gravity	—	—	> 1.1 × ULN

LLN = lower limit of normal value provided by the laboratory; SI = *Le Système International d'Unités* (International System of Units); ULN = upper limit of normal value provided by the laboratory.

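### Neither SAP has a change-from-baseline PCS criterion for QTcF or creatinine, so a large rise below the fixed limit is neither counted by arm nor flagged for the participant

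*SAP*

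**What the plan says.** The protocol leaves the laboratory and ECG PCS limits to the SAP (Protocol 9.1.5.2.2 and 9.1.5.2.4). The IBS-C and FC SAPs set the same ones.

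- **ECG (Section 11.4, Table 11-3).** "Electrocardiographic parameter values are considered PCS if they meet or exceed the higher-limit PCS criteria listed in" Table 11-3. The QTcF entry is "QTc(F) msec >480". There is no change column.
- **Laboratory (Section 11.2, Table 11-1).** Values are PCS "if they meet either the lower-limit or higher-limit PCS criteria listed in" Table 11-1. The creatinine entry is "Creatinine µmol/L — > 1.3 × ULN". Again there is no change column.
- **Vital signs (Section 11.3, Table 11-2).** "Vital sign values will be considered PCS if they meet both the observed-value criteria and the change-from-baseline criteria listed in" Table 11-2. The weight row has no observed-value limit, so weight is flagged on a 5% change alone.

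For ECG and laboratory values, three outputs depend on the PCS flag: the count and percentage by arm, the display of flagged participants, and the display of adverse events in flagged participants.

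Other outputs do not depend on it. For ECG, group statistics are planned for "QT interval, and QTc) and changes from baseline values at each assessment time point will be presented by study intervention group", and Section 11 includes the minimum and maximum among them. There is also an investigator interpretation shift table, and "A tabular display showing participants with postbaseline clinically significant ECG abnormalities according to the Investigator’s overall interpretation will be provided". For laboratory values, low/normal/high shift tables to the end of the Intervention Period are planned. Section 16.4 puts every assessment in the data listings. Section 11.1 plans separate AESI tables and listings.

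**The concern.** The protocol's AESI is volume depletion, electrolyte abnormality or ECG abnormality judged to be related to diarrhea (Protocol 8.3.1). A child can move a long way from his or her own baseline and still stay under a fixed limit.

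The IBS-C part has no placebo arm, so each child's baseline is an important internal reference. Some children aged 7 to 11 also receive doses above those that age group had in LIN-MD-63 (Protocol Table 2-2 and Section 4.3.2).

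If the PCS rows for QTcF and creatinine are near zero in every arm, a reader may take that as evidence that no large individual changes occurred. A fixed limit alone cannot show that.

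**Working it through.** The plan states no figure of its own here, so there is nothing to reproduce. The check has three steps: the threshold arithmetic, which needs only the documents; a sensitivity range over assumed baselines, which the documents do not give; and a look at which other outputs would show the change. The 60 ms rise and the doubling are illustrations and are not in the documents.

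**1. Thresholds**

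- QTcF: a rise of 60 ms is unflagged when baseline + 60 <= 480, that is, baseline <= 420 ms.
- Creatinine: a doubling is unflagged when 2 x baseline <= 1.3 x ULN, that is, baseline <= 0.65 x ULN.
- Fold-rise needed for a creatinine flag = 1.3 / (baseline/ULN): 2.6 at 0.5, 2.17 at 0.6, 1.63 at 0.8.

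The QTcF cut-off uses the strict inequality in Table 11-3. The sentence above that table also counts values equal to the limit, so a reading of exactly 480 ms is ambiguous.

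**2. Sensitivity to baseline (assumed normal)**

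P(flagged after a 60 ms rise) = 1 - Phi((480 - mean - 60)/SD):

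| Baseline mean QTcF | SD 15 | SD 20 | SD 25 |
|---|---|---|---|
| 390 ms | 2% | 7% | 12% |
| 405 ms | 16% | 23% | 27% |
| 420 ms | 50% | 50% | 50% |

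For example, at 405 and 20: (480 - 465)/20 = 0.75, and 1 - Phi(0.75) = 0.23. For a 40 ms rise the same grid gives 0% to 21%. At a mean of 430 ms the balance reverses: only 25% to 35% of 60 ms rises are unflagged.

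Share of creatinine doublings left unflagged = Phi((0.65 - mean)/SD), with baseline in multiples of ULN and SD 0.08 to 0.15:

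| Baseline mean | Unflagged |
|---|---|
| 0.50 | 84% to 97% |
| 0.60 | 63% to 73% |
| 0.65 | 50% |
| 0.70 | 27% to 37% |
| 0.80 | 3% to 16% |

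With baselines uniform from 0.3, 0.4, 0.5 or 0.6 up to 1.0 x ULN, the unflagged share is 50%, 42%, 30% or 12.5%.

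**3. What the other outputs show**

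- A doubling from 0.6 to 1.2 x ULN is not PCS, but it is a normal-to-high shift if present at the end of the Intervention Period.
- Only a doubling from 0.5 x ULN or less can stay within the upper limit and miss the shift table too. With the uniform baselines above, that share is 29%, 17%, 0% and 0%.
- For QTcF there is no normal/high shift table on the measured value. The maximum change shows the largest analysed rise in an arm, but not how many children had one or who they were. The listings hold the values unsorted by any change rule.

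**The case against.** Four points on the other side have weight.

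- **The changes are not hidden.** A reader might infer that a sub-limit rise disappears into group means. It does not: maximum changes, full listings, the laboratory shift table and the investigator's ECG reading all remain, and readable ECGs received by the vendor go to cardiologist over-read (Protocol 8.2.3). This stands, and it reduces the gap to the lack of a count and a participant flag.
- **AESI capture does not use PCS.** A reader might infer that AESIs would be missed. They are identified by investigator or sponsor judgement and reported separately, and the definition names neither creatinine nor QTc. This stands. Volume depletion also has postural blood pressure and pulse criteria in Table 11-2.
- **The vital-sign contrast is weak.** Most change criteria in Table 11-2 must be met together with an observed-value limit, so they narrow a flag rather than trigger one. This stands for every row except weight, which is the only precedent for a change-only row.
- **No cut-off is supported by the documents.** Neither 60 ms nor any creatinine ratio appears in them. This stands, so the sponsor must choose and justify the value. It does not remove the gap, since any change rule would supply a count the plan now lacks.

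It is also true that these tables are descriptive and that ECGs are scheduled only at screening and end of treatment. There will usually be one post-dose change per child, so a change rule is simple to apply but adds limited information.

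**Conclusion.** The gap is real but narrow. Neither SAP has a categorical change-from-baseline criterion for QTcF or creatinine. A 60 ms rise from a baseline of 420 ms or less, and a doubling from 0.65 x ULN or less, are left out of all three PCS outputs. That much follows from the documents alone.

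The documents do not support saying that such changes usually go unflagged. For QTcF it is plausible under the assumed means of 390 to 420 ms (2% to 50% flagged), but those means are assumptions. For creatinine the answer reverses once typical baselines exceed 0.65 x ULN, and the shift table recovers part of what PCS misses.

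The QTcF part therefore merits a change as a cheap improvement. The creatinine part is weaker and optional.

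**What to change.** In Table 11-3 of both SAPs, keep > 480 ms and add a separate QTcF row based on increase from baseline alone, for example > 60 ms, with the sponsor to confirm and justify the cut-off. Tabulate and list it as for the other PCS rows, in the same change-only form as the weight row in Table 11-2. State that its denominator is participants with a baseline and at least one postbaseline value, because a change criterion cannot be met at baseline. In the same edit, make the wording of Section 11.4 and the inequality signs in Table 11-3 agree.

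Optionally, add a creatinine ratio-to-baseline row to Table 11-1, again with a cut-off chosen by the sponsor.

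The cost is SAP text and programming on data already collected. The protocol defers these criteria to the SAP, so its text need not change. The downside is that a few more participants will be flagged, some because of measurement variability. The documents do not allow that number to be estimated.

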11.5 Other Safety Parameters

11.5.1 Potential Hy's Law

Potential Hy's Law criteria within a 24-hour window is defined by a post baseline elevation of ALT or AST $\geq 3x$ ULN, along with TBL $\geq 2x$ ULN and a non-elevated ALP $< 2x$ ULN, all based on blood draws collected within a 24-hour period.

Participants who meet the potential Hy's Law criteria from the first dose of study drug to within 30 days after the last dose of study intervention will be summarized. Supportive tabular displays will also be provided.

12 Health Outcomes Analyses

Not applicable.

13 Interim Analysis

For IBS-C participants in this study, no interim analysis is planned.

14 Determination of Sample Size

The sample size of at least 50 randomized participants per arm (at least 100 randomized participants in total) for IBS-C participants in this study was planned to inform the prescriber regarding the safe and efficacious use of linaclotide doses in this patient population. The planned sample size is not driven by any statistical consideration. This section provides the estimated Bayesian powers for the primary analysis of the primary endpoint in IBS-C portion of this study for the planned sample size.

Extrapolation from IBS-C adult studies (MCP-103-202 [Phase 2b], LIN-MD-31 [Phase 3], and MCP-103-302 [Phase 3]) was performed using Bayesian methodology with the primary efficacy endpoint of 6/12 week APS + 2 responder endpoint (as defined in Section 10.1). APS + 2 responder rates for treated individuals from the adult IBS-C population in Phase 2b study MCP-103-202 and Phase 3 pivotal studies LIN-MD-31 and MCP-103-302 were used to form a prior probability distribution for the pediatric APS + 2 response rate. This prior was down-weighted. Responder data from LIN-MD-64 were simulated using the down-weighted prior and the lower 2.5 percentile of posterior samples compared separately against the pooled placebo rate and the upper limit of 95% CI (2-sided) of pooled placebo rate from the adult contributing studies. The probabilities (Bayesian powers) that the lower 2.5 percentile of the linaclotide responder rate being greater than the pooled placebo rate from contributing adult studies, for different sample sizes and effective sample sizes (with associated down-weight factors) are provided in Table 14-1. Similarly the probabilities (Bayesian powers) that the lower 2.5 percentile of the linaclotide responder rate being greater than the upper limit of the 95% confidence interval of the placebo responder rate from contributing adult studies are also provided in Table 14-2.

With the consideration of a modest weight of 0.017 on the prior (equivalent to 15 new subjects from the adult IBS-C studies), the planned sample size of 50 IBS-C participants per arm should sufficiently describe the efficacy in pediatrics when contextualized using the pooled placebo rate from adult contributing studies.

The details of simulation codes to generate Bayesian powers in Table 14-1 and Table 14-2 are provided in Appendix 1.

Table 14-1. Bayesian Power Estimates by Sample Size and ESS (vs. the Responder Rate of the Adult Placebo Response, 0.16*)

	N/Arm=30	N/Arm=40	N/Arm=50
ESS=12 (w = 0.0135)	0.763	0.808	0.836
ESS=15 (w = 0.017)	0.865	0.873	0.854
ESS=18 (w = 0.020)	0.865	0.903	0.904
ESS=24 (w = 0.027)	0.943	0.954	0.964

ESS (Effective Sample Size) is calculated as the number of subjects used to derive the prior distribution multiplied by the down weight (w).

* Based on pooled adult placebo data from Phase 2b study MCP 103 202 and Phase 3 pivotal studies LIN MD 31 and MCP 103 302.

Table 14-2. Bayesian Power Estimates by Sample Size and ESS (vs. the Upper Limit of the 95% CI (2-sided) of the Adult Placebo Response, 0.18*)

	N/Arm=30	N/Arm=40	N/Arm=50
ESS=12 (w = 0.0135)	0.674	0.762	0.741
ESS=15 (w = 0.017)	0.809	0.769	0.809
ESS=18 (w = 0.020)	0.800	0.855	0.828
ESS=24 (w = 0.027)	0.895	0.925	0.895

ESS (Effective Sample Size) is calculated as the number of subjects used to derive the prior distribution multiplied by the down weight (w).

* Based on pooled adult placebo data from Phase 2b study MCP 103 202 and Phase 3 pivotal studies LIN MD 31 and MCP 103 302.

15 Statistical Software

Statistical analyses will be performed using version 9.4 (or newer) of SAS on a Linux operating system.

16 Data Handling Conventions

16.1 Visit Time Windows for Safety Analyses

Table 16-1 presents the visits assigned for safety analyses and the corresponding range of study intervention days (window) during which an actual visit may occur.

Table 16-1. Visit Time Windows

Derived Visit	Scheduled Visit Day^a	Window
Baseline	Day 1	Days ≤ 1
Week 2 Visit	Day 15	Days [2, 21]
Week 4 Visit	Day 29	Days [22, 42]
Week 8 Visit	Day 57	Days [43, 70]
Week 12 Visit	Day 85	Days [Day 71, max (last dose day+1, Visit 7 date)]
Post-intervention Visit	Day 92	Days \geq max (last dose day+1, Visit 7 date)+1
End of Double-Blind Intervention Period ^b	Final or Termination Visit during the double-blind Intervention Period	

- Relative to the date of the first dose of double blind study intervention. Day 1 = the date of the first dose of double blind study intervention. There is no Day 0 or Week 0.
- Presented in analysis tables for safety parameters, including but not limited to electrocardiograms, clinical laboratory values, and vital signs.

Participants who rollover to the long-term safety study, LIN-MD-66, before the EOS visit (i.e. Visit 8, post-intervention visit) are not required to have this EOS visit or post-intervention visit.

If the assessment date (if the assessment date is unavailable, use visit date instead) is on or after the date of the first dose of study intervention, the study day is calculated by assessment date - date of the first dose of study intervention + 1. If the assessment date is before the date of the first dose of study intervention, the study day is calculated by assessment date - date of the first dose of study intervention. Therefore, a negative day indicates a day before the start of the study intervention.

If a participant has 2 or more visits within the same window, the last visit with a non-missing value will be used for analysis.

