- a Study procedures for screening in LIN-MD-66 can be combined with End of Treatment (EOT)/Week 12 Visit (Visit 7) for Study LIN-MD-64.
- b Participants who rollover to the long-term safety study, LIN-MD-66, before the EOS Visit (Visit 8) are not required to have this visit.
- c Participants must complete at least 12 weeks (84 days) of study intervention before arriving at the study site for the EOT/Week 12 Visit (Visit 7). All randomized participants who prematurely discontinue from the study intervention, regardless of cause, should complete assessments at this EOT/Week 12 Visit (Visit 7).
- d The parent/guardian/legally authorized representative must provide written informed consent and the participant must provide assent before the participant's enrollment in the study. If a parent or legal guardian is also the participant's caregiver, he or she will be asked to sign a combined parent and caregiver written informed consent. Caregivers other than parent or legal guardian must provide written informed consent.
- e Prior to dosing, the investigator or appropriate site staff member will assess if Rome IV criteria for Child/Adolescent FC (FC and IBS-C participants) or Rome IV criteria for Child/Adolescent IBS (IBS-C participants) was met and record the outcome in the eCRF. Eligibility for the study is not based on this assessment.
- f Eligibility report must be run prior to randomization.
- g During the Screening Period, participants and their caregivers will receive information regarding lifestyle modifications (refer to Section 5.3 for details). There should be at least a 2-week interval between discussing the lifestyle modifications during the Screening Period and the participant's entry into the Preintervention Period.
- h Physical examinations will be performed by medically qualified site personnel and may be repeated at the investigator's discretion. If fecal impaction (as defined in footnote i) is documented during an optional repeat physical examination, the Study Physician must be notified.
- i Fecal impaction is defined as a hard mass in the lower abdomen identified on physical examination or a dilated rectum filled with a large amount of stool on rectal examination. If a rectal examination is performed, the medically qualified site personnel should assess for and document the presence of anal wink and normal anal tone.

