Participants who discontinue from the study and do not return to the study site for EOT Visit must be requested in writing to return to the study site for procedures required at the EOT Visit as defined in the SoA and return any unused study intervention. A copy of the letter, together with the source documentation, will be kept in the investigator's files. The reason for premature discontinuation from the study will be recorded on the Study Termination Page of the eCRF. Study site staff will be contacted by the sponsor after each premature discontinuation to ensure proper characterization of the reason for discontinuation is captured.

See the SoA for data to be collected at the time of study intervention discontinuation and follow-up and for any further evaluations that need to be completed.

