#### **10.10.8. End of Study Visit /Postintervention Follow-up (Visit 8)**

Participants will not receive study intervention during the Postintervention Period.

Participants that complete LIN-MD-64 have the option to enroll into the open-label, long-term safety study, LIN-MD-66, if they meet the eligibility criteria. Participants will be considered to have completed LIN-MD-64 if he/she has completed 12 weeks of double-blind study intervention, the EOT visit (Visit 7), and the EOS visit (Visit 8). However, this EOS visit is not required for participants who enroll into the open-label, long-term safety study LIN-MD-66 prior to that visit.

During this EOS Visit (Visit 8), the following procedures will be performed:

- Obtain weight; temperature (oral, rectal, or tympanic) and respiratory rate; and postural vital signs (supine and standing systolic and diastolic BP and pulse rate)
- Review any AEs occurring since the last visit
- Review eDiary completion
- Review concomitant medications
- Review use of protocol-permitted rescue medication dispensed in IWRS where applicable.

- Review rescue medication compliance and accountability.
- Rescue medication will be returned
- eDiary device will be returned

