withdrawn participant's Intervention Period and all subsequent Intervention Period weeks will be missing for that participant.

Table 16-3 below presents the weekly periods assigned for the efficacy analysis of the participant weekly diary data related to global severity items and global change items.

Table 16-3. Analysis Time Windows for Efficacy Analysis - Weekly Questions

Analysis Week	Begins ^a	Ends ^a
Week -2	Visit 2 day	Visit 2 day + 7
Week -1 (Baseline)	Visit 2 day + 8	Day 1
Week 1	Day 2	Day 8
Week 2	Day 9	Day 15
Week 3	Day 16	Day 22
Week 4	Day 23	Day 29
Week 5	Day 30	Day 36
Week 6	Day 37	Day 43
Week 7	Day 44	Day 50
Week 8	Day 51	Day 57
Week 9	Day 58	Day 64
Week 10	Day 65	Day 71
Week 11	Day 72	Day 78
Week 12	Day 79	last dose date +1
Post-intervention	Day of last dose date + 8	Day of end of study visit

- a. Begin and end of each week from Week 1 onwards are relative to the date of the first dose of double blind study intervention. Day 1 = the date of the first dose of double blind study intervention. There is no Day 0 or Week 0. End of Week 1 to Week 12 will be day of last dose + 1 or corresponding end day in table whichever comes earlier.

Participants who rollover to the long-term safety study, LIN-MD-66, before the EOS visit (i.e. Visit 8, post-intervention visit) are not required to have the EOS visit or post-intervention visit.

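### The Week 2, 4 and 8 safety windows in Table 16-1 of both SAPs do not close when treatment stops, so an early stopper's off-drug visit can become the on-treatment week value

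*SAP*

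**What the plan says.** Section 16.1 is the same in both SAPs. Write C for the later of last dose day + 1 and the Visit 7 date. Table 16-1 then assigns safety visits as follows:

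- Week 2: Days 2 to 21
- Week 4: Days 22 to 42
- Week 8: Days 43 to 70
- Week 12: Day 71 to C
- Post-intervention: from "max (last dose day+1, Visit 7 date)+1" onward, that is C + 1, with no minimum day

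The rule for several visits in one window is "If a participant has 2 or more visits within the same window, the last visit with a non-missing value will be used for analysis". Section 16.1 has no sentence that shortens Weeks 2, 4 and 8 for an early stopper, and none that gives Post-intervention priority.

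The efficacy windows in section 16.2 are treated differently. A withdrawn participant's diary week is cut at the end of that participant's intervention period. The note to Table 16-3 states "End of Week 1 to Week 12 will be day of last dose + 1 or corresponding end day in table whichever comes earlier".

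For vital signs, section 11.3 has PCS values "tabulated by study intervention group for the double-blind Intervention Period and Postintervention Period separately". Section 16.4 uses every postbaseline assessment for PCS determinations.

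**The concern.** For anyone who stops well before Day 70, the fixed windows and the Post-intervention window overlap. A visit made after treatment has ended can carry two labels, and the last-visit rule then prefers it to the earlier visits in the same on-treatment week. The Week 12 row and both efficacy schemes are truncated at the end of treatment, so the omission for Weeks 2, 4 and 8 does not look deliberate.

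At stake is whether a by-visit table headed Week 4 describes children on treatment. Early stoppers matter for safety out of proportion to their number: Protocol section 7.1.1 requires discontinuation for treatment-related volume depletion, electrolyte or ECG events linked to diarrhea. A value taken after such a child has stopped is the wrong one to show under an on-treatment week.

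**Working it through.** **Inputs.** The windows and C come from Table 16-1. Visit 8 is scheduled 7 to 14 days after the end-of-treatment visit (Protocol Table 1-1), so Visit 8 day = Visit 7 day + g, with g = 7 to 14. For the enumeration I assume the last dose is the day before Visit 7, so C = Visit 7 day.

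**1. The plan's own case.** A completer has last dose Day 84 and Visit 7 Day 85, so C = 85. Days 15, 29, 57, 85 and 92 fall in Week 2, Week 4, Week 8, Week 12 and Post-intervention, one window each. The table works as intended here.

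**2. When a visit is double-assigned.** A visit on day d is in Post-intervention if d > C, and in a fixed week window if d ≤ 70. Both hold when C < d ≤ 70. For Visit 8 this needs Visit 7 day ≤ 70 − g:

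- g = 7: Day 63 or earlier
- g = 14: Day 56 or earlier

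An unscheduled visit sooner after Visit 7 can overlap with C as late as Day 69.

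**3. Examples.**

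| Last dose | Visit 7 | Visit 8 | Windows for Visit 8 | Consequence |
|---|---|---|---|---|
| Day 30 (on-drug visit Day 29) | Day 32 | Day 39 | Week 4 and Post-intervention | Days 29, 32 and 39 are all in Week 4; Day 39 is used |
| Day 18 | Day 20 | Day 27 | Week 4 and Post-intervention | Week 4 holds only an off-drug value |
| Day 64 | Day 66 | Day 73 | Post-intervention only | No overlap |

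**4. How much of the calendar is exposed.** Take Visit 7 on Days 3 to 84 (82 days) and eight values of g: 82 × 8 = 656 combinations.

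- Double-assigned for a given g: Visit 7 on Days 3 to 70 − g, which is 68 − g days. Summed over g = 7 to 14: 8 × 68 − 84 = 460, or 460/656 = 70%.
- Visit 8 in the same week window as Visit 7, so displacing it: (19 − g) + (21 − g) + (28 − g) = 68 − 3g. Summed: 544 − 3 × 84 = 292, or 45%.
- The remaining 460 − 292 = 168 fall in a later week window, which then contains no on-treatment visit at all.

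If Visit 7 is restricted to Days 2 to 70 (69 days), a visit 7 days later lands in a fixed window on 62 of 69 days and in Visit 7's own window on 48 of 69. At 14 days the counts are 55 and 27. All of these are shares of possible days, not of participants.

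**5. With a cap.** If each week window ends at the earlier of its listed last day and C, no day after C can be in a week window. The 460 becomes 0. In the first example, Day 39 is Post-intervention only.

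**6. Which outputs are touched.** Protocol section 10.10.8 lists for Visit 8 "Obtain weight; temperature (oral, rectal, or tympanic) and respiratory rate; and postural vital signs", with no scheduled laboratory tests or ECG. By-visit vital-sign tables (section 11.3) cover temperature, weight, respiratory rate, and supine pulse and blood pressure. Laboratory and ECG summaries are reached only through unscheduled visits. Protocol section 8.2.4 provides one route: clinically significant laboratory results up to 30 days after the last dose are to be repeated until they settle.

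**The case against.** The strongest reply is that this is a missing tie-break in a few descriptive rows. Much of it stands:

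- **Orthostatic effects are not hidden.** A reader might infer that on-drug postural blood pressure and pulse are overwritten. By-visit tables hold supine values only. Postural change enters through PCS criteria, and section 16.4 exempts PCS from the last-visit rule.
- **PCS events are not lost or understated.** For a child already in the denominator, counting a visit in both periods can only add an event or leave the count unchanged. Section 11.3 tabulates by period rather than by week label, so a programmer might well start the Postintervention Period at C + 1. The text does not say so.
- **Visit 8 attendance is not confirmed for early stoppers.** The documents send them to Visit 7 and exempt only rollover participants from Visit 8. They do not separately say that discontinuers attend it.
- **Visit 7 may itself be off drug.** In the first example Day 32 would still displace Day 29 after the cap. That follows from the plan's explicit choice to keep Visit 7 in the intervention period.

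A reader might also want a day limit on late Visit 7 data, because discontinuers who do not come back "must be requested in writing to return to the study site for procedures required at the EOT Visit". Last dose Day 24 and Visit 7 Day 75 would put results from 75 − 24 = 51 days off drug into Week 12. The documents do not support a particular cut-off. Laboratory and ECG PCS tables cover only the double-blind period, so moving late Visit 7 results would drop them from those counts, and Visit 7 is the only scheduled laboratory and ECG assessment after Day 1.

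None of this removes the overlap or supplies a rule that resolves it.

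**Conclusion.** The point holds in a limited form. On the literal text of both SAPs, a visit after C and on or before Day 70 belongs to two windows, and the last-visit rule makes an off-drug value the on-treatment week result. This is a stated rule giving a wrong by-visit value, not only a missing detail.

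The reach is narrow: by-visit summaries of supine blood pressure and pulse, weight, temperature and respiratory rate; laboratory and ECG summaries through unscheduled repeats only; and period assignment in the vital-sign PCS tables. Adverse events, AEs of special interest (AESIs) and completers are unaffected.

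The number of children cannot be derived from the documents. A reader might take an assumed 5 to 15% early stopping as the number affected (about 16 to 49 of 326 FC and 5 to 15 of 100 IBS-C participants). That is too high: it counts every early stopper, including those who stop too late for an overlap and those with no later visit. The 70% is a share of day combinations and rests on last dose the day before Visit 7 and on Visit 8 being attended on schedule. The change should be made because it is simple and leaves no choice to programming.

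**What to change.** Add one footnote to Table 16-1 in each SAP: every on-treatment window ends at the earlier of its listed last day and the later of last dose day + 1 and the Visit 7 date; visits after that are Post-intervention only. State that the same boundary separates the Intervention and Postintervention Periods in the vital-sign PCS tables. Leave the handling of Visit 7 as it is.

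The cost is a sentence or two per SAP and the matching window programming. It needs no new data, does not change completers' results, and takes no value out of PCS determination.
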